7.2.2 Clinical Procedures/Assessments

7.2.2.1 Adverse Event Monitoring

The Investigator or qualified designee will assess each subject to evaluate for potential new or worsening AEs as specified in the Schedule of Events and more frequently if clinically indicated. AEs will be recorded starting from the time that the first dose of study treatment is administered through the completion of the *Lm* surveillance period. Adverse and serious adverse events experienced during this period will be reported and recorded in the eCRF. Adverse experiences will be graded according to NCI CTCAE v 4.03 (see [Section 10.2](#)). Toxicities will be characterized in terms regarding seriousness, causality, toxicity grading, and action taken with regard to study treatment.

7.2.2.2 Physical Examination

The Investigator or qualified designee will perform focused physical examinations (PE) during the Prime Phase on Weeks 4 and 7, and during the Maintenance Phase on the Week 23 visit. Full physical exams should be performed on all other visits.

The “full” PE will include the following organ or body system assessments: skin; head, eyes, ears, nose, and throat; thyroid; lungs; cardiovascular; abdomen (liver, spleen); extremities; groin, axillary and neck lymph nodes; assessment for edema and/or ascites, and a brief neurological exam; Gynecologic exam: external genitalia, speculum exam of the vagina, digital exam of the vagina and digital exam of the rectum/anus.

The “focused” PE will include the following assessments: examination of all symptomatic areas as well as skin; head; lungs; cardiovascular; abdomen (liver, spleen); extremities; groin, axillary and neck lymph nodes; assessment for edema and/or ascites; neurological exam.

A clinically significant finding or a worsening in a PE finding from the previous visit in the opinion of the Investigator or qualified designee will be recorded in the eCRF and reported as an AE.

PEs may be performed more frequently, as clinically indicated. An “Unscheduled Visit” form will be used to record this information in the eCRF.

7.2.2.3 Vital Sign Measurements

The Investigator or qualified designee will measure and record vital signs (including blood pressure, pulse rate, respiratory rate, and temperature) at the Screening Visit, prior to each assigned study treatment administration and [REDACTED] following each study treatment infusion. Weight will be collected prior to each study treatment infusion. Height will be measured at Screening Visit only.

A clinically significant finding or a worsening in a PE finding from the previous visit in the opinion of the Investigator or qualified designee will be recorded in the eCRF and reported as an AE.

7.2.2.4 Performance Status

The Investigator or qualified designee will assess GOG performance status (see [Section 14.2 GOG Performance Scale](#)).

7.2.2.5 Pelvic Examination

The investigator or qualified designee will perform a pelvic exam which will include a speculum exam with bimanual pelvic and rectal examination. Cervical and vaginal cytology will be performed at Screening only unless deemed necessary by the treating physician.

7.2.3 Laboratory Procedures/Assessments

Laboratory tests will be performed within 3 days prior to each dose of study treatment administered. **The laboratory results must be reviewed by the Investigator or qualified designee and found to meet all defined dosing criteria in order for a subject to receive study treatment (See [Table 7 Laboratory Tests](#)).**

Subjects must also be thoroughly screened for an ongoing or active infection prior to each treatment infusion. Subjects whose pre-infusion CBC reveals leukocytosis may need additional evaluation (e.g. a urinalysis) to rule out an active infection. Subjects with documented ongoing or active infection must receive appropriate antibiotic treatment for their underlying infection and return to \leq CTCAE Grade 1 prior to dosing with study treatment. The Investigator should call the Sponsor to discuss a specific subject's case if there appears to be special circumstances which could result in resuming study treatment. In addition, the subject must also be at least 5 half-lives from their last dose of antibiotic.

Laboratory tests for hematology, chemistry, urinalysis, and others are specified in ([Table 7](#)).

Surveillance monitoring for the detection of *Lm* will be initiated at the completion of study treatment according to the protocol or at the time of study discontinuation, if earlier. See [Section 5.2.4 Follow-up Period](#) for further details. All blood cultures that grow *Lm* will be reported to FDA as part of the Adverse Event and Serious Adverse Event monitoring during the *Lm* surveillance period.

Table 7 Laboratory Tests

Hematology	Chemistry	Urinalysis	Other
Hematocrit Hemoglobin Platelet count WBC (total and differential) Red Blood Cell Count Absolute Neutrophil Count	Albumin Alkaline phosphatase Alanine aminotransferase (ALT) Aspartate aminotransferase (AST) Lactate dehydrogenase (LDH) C-Reactive Protein (CRP)* Carbon Dioxide ‡ (CO₂ or bicarbonate) Creatinine Calcium Chloride Erythrocyte Sedimentation Rate (ESR)* Glucose Potassium Sodium Total Bilirubin Direct Bilirubin (If total bilirubin is elevated above the upper limit of normal) Total Protein Blood Urea Nitrogen	Blood Glucose Protein Specific gravity Microscopic exam (If abnormal) Urine pregnancy test †	Serum β-human chorionic gonadotropin† (β-hCG)† Lm Surveillance blood cultures*

† Perform on women of childbearing potential only. If urine pregnancy results cannot be confirmed as negative, a serum pregnancy test will be required.

‡ If considered standard of care in your region.

**Lm* surveillance Monitoring will include routine monitoring of CBC, CMP (including CRP, ESR) and blood cultures. All blood cultures positive for *Lm* will be reported to FDA as part of the Adverse Event and Serious Adverse Event monitoring during the *Lm* surveillance period.

7.2.5 Efficacy Assessments

The efficacy endpoints of the study are Disease Free Survival (DFS) and Overall Survival (OS). They will be assessed as follows:

7.2.5.1 Histologic/Cytologic Assessment for Disease Recurrence

Suspicion of recurrence can be based upon multiple clinical factors such as an abnormal physical and/or pelvic exam, including cytology and/or imaging. A biopsy and histologic examination and/or cytologic examination of a Fine Needle Aspirate (FNA) of a new suspected lesion is required to confirm disease recurrence when it is feasible in the opinion of the investigator.

A cytologic examination of a PAP smear is not acceptable to make a determination of recurrence however a cytologic examination of a Fine Needle Aspirate (FNA) of a new suspected lesion is acceptable to make a determination of recurrence.

7.2.5.2 Radiographic Assessments for Disease Recurrence

Baseline scans must be performed within 28 days of first study treatment infusion and must include contrast-enhanced CT of the chest and abdomen, plus a contrast-enhanced MRI of the pelvis; or a fluorodeoxyglucose (FDG) PET/CT of the chest, abdomen and pelvis. When PET/CT is used, the CT component of the PET/CT must be of diagnostic quality. Each anatomic area must be assessed using the same method at all time points (baseline and post-baseline) for each subject.

Note: The only acceptable methods of imaging the pelvis are MRI and PET/CT.

For subjects who have a medical contraindication to IV iodinated CT contrast, a non-contrast CT of the chest is acceptable; however, the abdomen must be imaged using a contrast-enhanced MRI. A non-contrast CT of the abdomen is not acceptable.

7.2.5.2.1 Unscheduled Radiographic Assessments

The schedule for radiographic assessments is detailed in [Section 7.1](#) - Schedule of Events. Unscheduled radiographic assessments can occur and are based upon the clinical judgment of the investigator. Reasons for an unscheduled assessment may include, but are not limited to, clinical deterioration, subject complaint and/or findings stemming from a physical examination.

Any unscheduled imaging assessment should be analyzed by the site for recurrence and labelled in the eCRF as an “Unscheduled Visit.” This assessment will also be submitted to the central imaging laboratory for evaluation. If the unscheduled imaging assessment occurs within 2 weeks of a scheduled visit, the unscheduled images should be evaluated with the nearest scheduled timepoint images. If disease recurrence is not confirmed on the evaluation of the images obtained at an unscheduled timepoint and within 2 weeks of a scheduled timepoint assuming all of the required scans were performed during the Unscheduled Visit then performing an additional radiographic assessment the next scheduled timepoint is not necessary.

7.2.6 Other Procedures

7.2.6.1 Withdrawal/Discontinuation and End of Study Visit

7.2.6.1.1 Discontinuation during Treatment Period Due to Disease Recurrence

When a subject meets a reason for discontinuation due to disease recurrence prior to the completion of the Treatment Period (Prime + Maintenance Phases), an End of Study (EOS) visit will be conducted and all applicable assessments, including physical examination, vital signs, performance status, pelvic examination, hematology and chemistry profile, urine dipstick, pregnancy test, as applicable, tumor imaging, dispense course of oral antibiotic, and [REDACTED] should be performed. Any AEs that are present at the time of discontinuation should be followed in accordance with the safety requirements outlined in [Section 10](#). The subject will enter the Post-Disease Recurrence Period and *Lm* Surveillance Period will be initiated at this time.

7.2.6.1.2 Early Discontinuation

Early discontinuation is defined as discontinuation during the treatment period for a reason other than disease recurrence. During the Study Treatment Period, when a subject meets a reason for discontinuation other than disease recurrence prior to the completion of the Treatment Period (Prime + Maintenance Phases) all applicable DFS assessments (i.e.: tumor imaging, pelvic examinations, and [REDACTED]) should be performed in accordance with the Visit Schedule until early study termination, 6 years from the date of enrollment, disease recurrence, or death, whichever comes first. Any AEs that are present at the time of discontinuation should be followed in accordance with the safety requirements outlined in [Section 10](#). The subject will enter the Follow-up Phase and the *Lm* Surveillance period will be initiated. Oral prophylactic antibiotics will be administered.

In subjects who have not experienced disease recurrence, physical exams, pelvic exams, and tumor imaging will occur at Weeks 12, 24, 36, and 48 during the first year (from date of enrollment) on trial, until early study termination, whichever comes first. During the second year, pelvic exams and tumor imaging will occur every 3 months (± 1 week), and then every 6 months (± 1 week) thereafter for four years, or until early study termination, whichever comes first. [REDACTED] so they coincide with the scheduled visits to assess tumor imaging and pelvic exams and with the

End of Study visit, which will occur 6 years from date of enrollment, or until early study termination, whichever comes first.

7.2.6.1.3 Discontinuation during the Follow-up Phase

During the Study Treatment phase, when a subject meets a reason for discontinuation from treatment, the EOS Visit should be conducted, after which the subject will enter the *Lm* Surveillance Period and will continue in accordance with the protocol requirements. During the Follow-up Phase, reasonable efforts should be made to have the subject contacted remotely and report any AEs that may occur during this phase.

7.2.6.1.4 Withdrawal of Informed Consent

In the event that any subject withdraws from the study treatment prior to completion, regardless of reason, reasonable efforts should be made to have the subject return for an EOS visit to have applicable assessments completed. The date the subject discontinued the study and specific reason for discontinuation will be recorded in the eCRF.

7.2.6.1.5 Blinding/Unblinding

Blinding of treatment assignment is critical to the integrity of this clinical study. However, in the event of a medical emergency or pregnancy in an individual subject in which knowledge of the investigational product is critical to the subject's management, the blind for that subject may be broken by the investigator during the study. The subject's safety takes priority in determining if a treatment assignment should be unblinded during the study.

Before breaking the blind of an individual subject's treatment, the investigator should determine that the unblinded information is necessary (i.e. that it will alter the subject's immediate management, as in the case with subjects who discontinue due to the development of sensitivity to Bactrim). In many cases, the problem may be properly managed by assuming that the subject is receiving active product (ADXS11-001) and treated accordingly. It is highly desirable that the decision to unblind treatment assignment during the study be discussed with the Medical Monitor, but the investigator always has ultimate authority for the decision to unblind during the course of the study. The Principal Investigator should only call for emergency unblinding during the study AFTER the decision to discontinue the subject has been made.

For subjects who are receiving treatment and have not progressed, the Sponsor, subjects, investigator and site staff will be blinded to the study drug. Each investigative site must assign an unblinded pharmacist/designee, and an unblinded site monitor will be assigned by sponsor to provide oversight of drug supply and other unblinded study documentation. The Sponsor's central protocol team (including but not limited to clinical, statistics, data management) will remain blinded.

For this study, the method of unblinding is through the IVRS. For information on how to unblind for emergency, please consult the IVRS manual. In cases of accidental unblinding during the study, contact the Medical Monitor and ensure every attempt is made to preserve

the blind my minimizing the total amount of individuals that may become unblinded. Any request to unblind a subject for non-emergency purposes during the blinded portion of the study is required to be discussed with the Medical Monitor.

8 EVALUATION CRITERIA

8.1 Assessment of Disease

Assessment of disease will be performed to evaluate for the development of new disease, and will include:

- Physical exam
- Pelvic exam
- Tumor imaging
- Confirmatory biopsy (when it can be safely achieved in the opinion of the investigator)

8.1.1 *Assessment of Disease Free Survival using Radiological Imaging Methodology*

The primary endpoint of the study is DFS; therefore, the use of contrast-enhanced CT and MRI or PET/CT scans is to achieve the primary objective of identifying disease recurrence. RECIST 1.1 criteria is an accepted method for determining PFS in patients with metastatic disease where a primary goal of the study is to assess the ability of a drug to reduce or eradicate a tumor which was identified using radiological imaging. However, the patients who will be enrolled in this study will be unlike those enrolled in the majority of the studies which have used RECIST 1.1 because they must have no measurable or non-measurable disease at the baseline imaging assessment in order to be eligible to participate in the study. In addition, a primary objective of the study is to prevent tumor recurrence in accordance with the definitions provided in the following sections and not to achieve a tumor “response.” Therefore, this study will only evaluate the ability of ADXS11-001 to prevent tumor recurrence and accordingly the only relevant designation for each timepoint measured by radiological imaging will be either “recurrence” or “no recurrence.” As a result, modifications to the way that the RECIST 1.1 criteria will be implement are needed. The modifications to the way the RECIST criteria are applied are justified because this study population has: (1) has already received treatment for their cancer; (2) has no measurable or non-measurable disease by RECIST 1.1 criteria following CCRT with curative intent to follow during the study; (3) will be evaluated only for disease recurrence and (4) the results from a biopsy of the tumor being evaluated will be used as confirmation of disease. The intended “spirit” of RECIST 1.1 will be employed by using the terms and measurement criteria when they apply to this study and patient population.

A detailed description of tumor imaging assessments is provided below as well as in the Imaging Review Charter.

8.2 Determination of Disease Recurrence

The following criteria define the methodology which can be used to define disease recurrence.

- Clinical deterioration alone **cannot** be utilized as the sole determinant of recurrence and needs to be confirmed by either imaging or confirmatory biopsy.
- Results from the physical and/or pelvic exam, including cytologic assessment of a PAP smear, **cannot** be utilized as the sole determinant of recurrence and need to be confirmed by either radiographic imaging or confirmatory biopsy/fine needle aspirate of a suspected lesion.
- Results from biopsy/FNA of a suspected lesion can be utilized as the sole determinant of recurrence. However, results from radiographic imaging as determined by independent radiology review can only be utilized as the sole determinant of recurrence in the event that a tissue confirmation is not medically feasible in the opinion of the investigator. In cases where radiologic imaging confirms disease recurrence and a biopsy/FNA was obtained of the tumor being evaluated by imaging which is negative, then the subject will be considered to have disease recurrence. Histopathologic or cytologic assessment of tumor can occur by local lab.

8.2.1 Definition of Recurrence

The determination of recurrence must occur by definitive pathologic tissue confirmation (e.g., biopsy/fine needle aspirate). However, in those cases where it is not medically feasible to obtain a tissue sample then radiographic evidence, when confirmed by independent radiology review, will be used to determine recurrence.

8.2.1.1 Pathologic Definition of Recurrence

If a suspected lesion, especially in a previously irradiated field, is evaluated by histopathologic or cytologic examination and determined to be positive by biopsy/fine needle aspirate then the subject will be deemed to have progressed. Evaluation of suspected tumor material will occur at the site by a qualified pathologist.

8.2.1.2 Types of Radiographic Assessments

Three types of radiologic assessments will be performed in this study.

- (1) Site Reads – These are performed on all subjects at baseline and follow-up time points. The site reads are used primarily for subject management.
- (2) Confirmation of Recurrence Reads – These reads are performed by a small, limited pool of independent radiologists trained on the criteria and with expertise in radiologic evaluation of this subject group. If the results of the Site Read demonstrate recurrent disease (RD,) the images are electronically transmitted to the imaging core lab and within 72 hours from receipt the

results of an independent Confirmation of Recurrence (COR) will be transmitted to the site. The role of this reader is very targeted – to ONLY confirm or not confirm disease recurrence. The purpose of this assessment is to prevent subjects from being removed too early before true recurrence has actually occurred.

- (3) Blinded Independent Read – Each subject will be separately evaluated by two readers for the RD parameters. When the two readers disagree on the presence or date of recurrence, a third expert reviewer (the Adjudicator) will review all results and select to agree with either reader A or B. The purpose of this read is to confirm RD. A separate radiology charter provides detailed information on all aspects of the radiographic assessments to be utilized for this protocol including adjudication. An independent radiology review will be conducted to confirm recurrence for all subjects. The independent radiology review will both an independent efficacy review and an independent review of COR.

In summary:

- The objective of the independent efficacy review is to prospectively determine when a subject enrolled in the study has developed a new tumor(s) that qualifies them for the recurrence determination. Expert and trained independent efficacy reviewers will interpret the images for the radiology review with no clinical information available. The independent efficacy review will provide the Sponsor with an assessment of the Time Point Response (TPR; NOTE: TPR will be limited to Recurrent Disease, [RD], non-RD, or Unable to Evaluate [UE] only; refer to [Section 8.2.1.4](#)) and the Date of Recurrence (if applicable) for each subject enrolled in the study.
- Separately, the independent COR review will provide the Sponsor and the investigator with a rapid confirmation of site-determined radiographic disease recurrence in instances when radiographic disease recurrence is suspected by the site radiologist. The purpose of this COR process is to provide the site PI with the best possible information regarding radiographic disease recurrence
- The population under evaluation by the independent efficacy reviewers will include all subjects enrolled on the ADXS001-02 study. For the purposes of the COR review, the population under evaluation by the independent COR reviewers will be all subjects suspected of having radiographic disease recurrence by the site radiologist and whose images were submitted to the central imaging lab for expedited COR review.

All treatment decisions remain the responsibility of the investigator.

A flow chart for the Independent Radiology Review Methodology can be found in Appendix [14.6](#).

8.2.1.2.1 Date of Recurrence

The Date of Recurrence is defined as the date of the first time point when RD is determined.

8.2.1.2.2 Assessment Date Conventions

It is acknowledged that an assessment may include several methods of evaluation performed over a period of several days within a window of time around an expected assessment date.

The convention to be followed when assessing each time point will be to assign a single date to evaluations performed within that time point. The Time Point Response (TPR) date will be recorded as the date of the first radiographic evaluation included in the series for that assessment.

8.2.1.3 Definition of Non-Disease Recurrence

An assessment of non-recurrent disease (Non RD) will be made when the criteria for RD has not been met and the TPR is neither UE nor NA.

8.2.1.4 Radiographic Assessment of Time Point Response

[figure not shown]
Radiographic assessments at each time point will be based on the presence or absence of new lesions. The time point assessment will be classified as either non-RD, RD or UE. This TPR is assessed with reference to Baseline for the evaluation of RD. The TPR for each time point will still be determined even in cases where the prior time point demonstrates RD. In addition, if an identified new lesion subsequently becomes UE it will continue to be considered present and classified as a RD.

[Table 8](#) shows “Imaging Time Point Assignment of Response Including Biopsy Information.” In situations where a biopsy result is negative for tumor, but results from imaging demonstrate disease recurrence then the final determination of RD will be based on the imaging results. In situations where a biopsy result is positive for tumor, but results from imaging do not demonstrate disease recurrence, then the final determination of RD will be based on the biopsy results.

Table 8 Imaging Time Point Assignment of Response Including Biopsy Information

Time Point Imaging Response	Biopsy Result¹	Final Timepoint Imaging Response
RD	Not medically feasible	RD
	Positive for tumor	RD
	Negative for tumor	RD
UE	Not medically feasible	UE
	Positive for tumor	RD ¹
	Negative for tumor	UE
Non-RD	Not medically feasible	Non-RD
	Positive for tumor	RD ¹
	Negative for tumor	Non-RD

¹A biopsy result, which is positive for disease, dictates a final timepoint response of recurrent disease irrespective of the imaging response.

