5.2 Randomization and Treatment Plan

Subjects must initiate the Screening period within 14 weeks after the completion of CCRT (inclusive of brachytherapy, when applicable). The Screening Period is 28 days in duration and all examinations and assessments required by the protocol are expected to be completed within this period. Clinical laboratory assessments must be completed no more than 3 days prior to randomization to ADXS11-001 or placebo.

Eligible subjects will be randomized 1:2 to Arm A (placebo) or Arm B (ADXS11-001).

Study treatment (ADXS11-001 or placebo) will be administered on Day 1 of the Week 1 visit. Study treatment may be administered ± 3 days within Day 1 of each scheduled infusion for subsequent visits (e.g. Week 4, Day 1 and Week 7, Day 1 visits).

- Arm A: Placebo administered IV over approximately [REDACTED] every 3 weeks (Weeks 1, 4 and 7 only) for 3 doses (Prime Phase), thereafter, subjects will receive an additional dose every 8 weeks (Weeks 15, 23, 31, 39, and 47) for 5 doses (Maintenance Phase). The *total treatment* period will be approximately 1 year.
- Arm B: ADXS11-001 administered IV over approximately [REDACTED] every 3 weeks (Weeks 1, 4 and 7 only) for 3 doses (Prime Phase), thereafter, subjects will receive an additional dose every 8 weeks (Weeks 15, 23, 31, 39, and 47) for 5 doses (Maintenance Phase). The *total treatment* period will be approximately 1 year.

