5.2.1 Screening Period

The following evaluations will be performed to confirm subjects' eligibility:

- Informed consent
- Demographic information
- Medical, surgical, and cancer history
- Concomitant therapy review
- Adverse events review (collected from the time informed consent is obtained)
- Full physical examination
- Vital signs, height, weight
- Pelvic exam inclusive of cervical and vaginal cytology (**NOTE:** Exam should include a speculum examination with bi-manual pelvic and rectal examinations.)
- GOG performance status
- Routine Laboratory tests (hematology, coagulation profile, blood chemistry, urinalysis, pregnancy test): Subjects whose pre-treatment CBC reveals leukocytosis may need additional evaluation (e.g., UA, etc.) to rule out an active infection. Confirmed infection will result in a delay of study treatment and must be treated with appropriate antibiotic treatment. Screening labs must be performed within 3 days of dosing.

- Tumor Imaging: Baseline scans must be performed within 28 days of first study treatment infusion and must include contrast-enhanced CT of the chest, abdomen and a contrast-enhanced MRI or PET/CT of the pelvis. If a contrast-enhanced CT of the pelvis is performed, an MRI of the pelvis is still required.
 - The modality selected for a patient for imaging of the pelvis (either contrast-enhanced CT and MRI or PET/CT) must be used consistently for the patient throughout the study.
 - For subjects who have a medical contraindication to IV contrast, a contrast-enhanced MRI or PET/CT of the abdomen and pelvis may be performed. In these subjects, a non-contrast CT scan of the chest must also be performed.

NOTE: Please refer to the Imaging Manual for details regarding imaging requirements, including but not limited to, image acquisition, collection and submission of scans for independent radiology review.

- Inclusion/Exclusion Review: Results of all screening evaluations must be reviewed by the principal Investigator or qualified designee to ensure that all eligibility criteria have been satisfied prior to subject randomization.

[figure not shown]

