11.1 Sample Size Considerations

For a study involving a sample of subjects with the same distribution of stage as listed in (Table 9), the estimated probability of surviving disease-free for at least 4 years is approximately 50%. Thereafter, the probability of recurring or dying increases very slowly (2-3% per year). This study will be considered sufficiently mature for a final analysis when there are at least 184 subjects reported as having experienced either recurrence of their cancer or death due to any cause. This number of events provides 85% power for detecting a treatment hazard ratio (HR) of 0.620. The type I error will be set to 0.025 (accounting for interim analysis) for a one-tail test of the null hypothesis (HR=1) using stratified logrank procedure. A treatment hazard ratio of 0.620 is comparable to increasing the expected proportion alive and disease-free for at least 4 years from 0.500 to 0.651.

Table 9 Summary of Study Parameters and Targeted Sample Size

Design Parameter	
Type I error (1-sided)	0.025
Statistical power	0.85
Treatment: Reference allocation ratio	2:1
Interim analysis *	50% IT
Hazard ratio H_A	0.620
Percent increase in DFS at 4 yrs. H_A	0.151
Number of DFS events required**	184
Target accrual (N of subjects)***	450
Accrual duration****	55 months
Post-accrual follow-up duration****	20 months

*An interim analysis of safety and efficacy planned at 50% of the information time (IT)

**East version 5.4, H_A is the alternative hypothesis for power calculations.

***Assumes cumulative probability of recurring or dying on the reference treatment during the first 4 years is approximately 50%, and thereafter this probability does not increase. See Note on Target Accrual (below).

****The estimated duration of accrual and post-accrual follow-up depend on the expected average accrual rate and the number of investigative sites participating in the study. It is estimated that ~ 450 subjects will be enrolled in 55 months.

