11.2.2 Definition of Study Populations for Analyses

The primary analysis population for the primary efficacy endpoints will be based upon the intention to treat (ITT) principle population. The ITT population includes all subjects enrolled into this study regardless of their eligibility or compliance with their assigned treatment. Secondary efficacy endpoints will be reported for the ITT population. Analyses of adverse events will include all subjects enrolled into this study who initiated their assigned study treatment.

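### The independent read counts only new lesions, so growth of a lesion it already saw at baseline stays non-recurrent unless a biopsy is positive

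*Combined protocol and SAP*

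**What the plan says.** **Entry.** Exclusion 1 in Section 3.2 bars women who are not disease-free after chemoradiation. Section 5.2.1 leaves the check to the site: "Results of all screening evaluations must be reviewed by the principal Investigator or qualified designee". The same section mentions submission of scans for independent radiology review, but nothing in the text makes a central finding of no disease a condition of randomization. The rapid central confirmation read in Section 8.2.1.2 is triggered by suspected recurrence, not by the baseline scan.

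**Scoring.** Section 8.1.1 reduces RECIST 1.1 to recurrence or no recurrence, partly because the study population "has no measurable or non-measurable disease by RECIST 1.1 criteria following CCRT". Section 8.2.1.4 then gives the rule: "Radiographic assessments at each time point will be based on the presence or absence of new lesions", judged against baseline. Section 8.2.1.3 makes a time point non-RD when the criteria for RD are not met and it is otherwise evaluable.

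**Tissue.** Section 8.2.1 requires tissue confirmation of recurrence where feasible. Table 8 lets a positive biopsy override non-RD or unevaluable imaging.

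**Analysis.** The ITT population "includes all subjects enrolled into this study regardless of their eligibility". Sections 11.2.3 and 11.2.6 take the primary DFS time from independent radiology review, with death from any cause also an event. Under Section 8.2.1.2 the independent efficacy readers have no clinical information.

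**The concern.** A scoring rule that recognises only new lesions is sound if every woman is clear of disease at baseline. The plan has the site check that premise, has a different reader score the endpoint, and keeps in the analysis any woman for whom the premise fails. If the two readers disagree about the baseline scan, a lesion can enlarge without ever meeting the independent reader's criterion.

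Two women with the same clinical failure can then be classified differently because one lesion was visible at baseline and the other was not. The first woman may be censored. With 110 randomized of the 450 planned, and the 184-event target abandoned, each event carries more weight than the design intended.

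**Working it through.** **1. The plan's own figure.** The plan sets "at least 184 subjects reported as having experienced either recurrence of their cancer or death due to any cause" as maturity for the final analysis and states: "This number of events provides 85% power for detecting a treatment hazard ratio (HR) of 0.620". Inputs from Section 11.1: one-sided alpha 0.025, power 0.85, HR 0.62, 2:1 allocation.
- Fixed design: d = (z_alpha + z_power)² / [p(1−p)(ln HR)²] = (1.960 + 1.036)² / [(2/9)(0.478)²] = 176.8, so 177 events.
- With the originally planned look at 50% information and O'Brien-Fleming-type spending of alpha (0.025) and non-binding beta (0.15): 183.8, so 184.

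The stated 184 reproduces. This point is about how events are classified, not about that figure.

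**2. When the gap opens.**
- The site sees disease at baseline: the woman is excluded and there is no gap.
- Neither the site nor the independent reader sees it: its later appearance is a new lesion, scored RD, and there is no gap.
- The site does not call it disease but the independent reader sees it: later growth is not a new lesion, so imaging is non-RD.

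Only the third case is affected.

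**3. What Table 8 then does.**

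| Biopsy result | New lesion (imaging RD) | Baseline lesion has grown, no new lesion (imaging non-RD) |
|---|---|---|
| Positive | RD | RD |
| Not feasible | RD | non-RD |
| Negative | RD | non-RD |

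The last two rows treat the same biopsy result differently according to whether the lesion was visible at baseline. Section 8.2.1.4 covers a new lesion that later cannot be evaluated, but not a baseline lesion that enlarges.

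**4. Does the biopsy override reach primary DFS?** Section 8.2.1 and Table 8 say that a positive biopsy is recurrence. Sections 11.2.3 and 11.2.6 name independent radiology review and do not mention biopsy, and the efficacy readers see images only. The one sensitivity analysis that Section 11.2.6 describes concerns positive imaging with negative biopsy, which is the reverse case. Section 7.2.5.1 speaks of biopsy of a new suspected lesion, while Section 8.2.1.1 does not require the lesion to be new. The documents do not settle the question.

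**5. Size, as illustration only.** Women left non-RD = N × d × g × (1 − b), where N = 110 (Section 11). The rest are assumptions, since the documents give none of them: d, the share with a baseline lesion seen only by the independent reader, 5–15%; g, the share of these growing in place before any new lesion, 50–75%; b, the share with a positive biopsy that counts in DFS.
- Low end at b = 0: 110 × 0.05 × 0.50 = 2.75. High end: 110 × 0.15 × 0.75 = 12.4.
- b = 50%: 1.4 to 6.2. b = 80%: 0.6 to 2.5. b = 100%: 0.

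If the override does not reach primary DFS, b is in effect 0. A later new lesion or death lowers the number of events finally lost.

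**6. Effect on power.** Power = Φ(√(events × 2/9) × |ln 0.62| − 1.96), if events are lost equally in both arms without replacement.
- At 184 events: 0.864. With 5%, 10%, 20% and 30% lost: 0.846, 0.826, 0.781 and 0.725.
- For 110 women with an assumed 20 to 50 events: 0.171 to 0.357. With 20% lost: 0.145 to 0.296.

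**The case against.** The strongest reply is biopsy. A reader might infer that a woman whose missed residual disease grows in place is automatically non-recurrent until a separate lesion appears or she dies. The documents do not support that. Tissue is the required route wherever feasible (Section 8.2.1), a positive result can stand alone (Section 8.2), Section 8.2.1.1 specifically mentions previously irradiated fields, and Table 8 overrides non-RD imaging. Disease missed by both readers is also scored as new later. All of this stands and confines the certain gap to growth with a negative or infeasible biopsy.

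Second, the Imaging Review Charter, the Imaging Manual and the separate SAP are not in the text reviewed, and the review flow chart in Appendix 14.6 is not shown. Section 8.1.1 also says that RECIST terms and measurements are used where they apply. A baseline or growth rule may therefore exist elsewhere. That stands as a limit, but Sections 8.2.1.3 and 8.2.1.4 as written give non-RD, so any such rule needs to be cited there.

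Third, no bias towards either arm is shown. The baseline misread precedes treatment in a randomized, double-blind trial, and chance imbalance affects any baseline factor. This also stands: what remains is possible loss of events and inconsistent classification.

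Fourth, efficacy assessment ended at termination (31 July 2019, Section 11), so redefining the primary event now is a late change. That is a fair reason to allow the growth rule as a sensitivity analysis. The same stop also shortens the time in which a new lesion or death could still be observed.

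**Conclusion.** The point holds in a limited form. On imaging alone, growth of a lesion that the independent reader saw at baseline is non-RD by the stated rule. It remains so when biopsy is negative or not feasible, although a new lesion with the same biopsy result is RD. Separately, Sections 11.2.3 and 11.2.6 conflict with Section 8.2.1 and Table 8 on whether a biopsy-positive recurrence enters primary DFS, and these passages must be reconciled.

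The size is unknown. A reader might take 3 to 12 lost progressions from the illustration, but that is the result with no positive biopsies and rests wholly on assumed rates. With a counted biopsy rate of 50% to 80% the range is about 0.6 to 6, before later new lesions and deaths are allowed for. A material share of the primary events is therefore not established. The conclusion that only the site confirms disease-free entry rests on the absence of a central step in the available text. The point merits correction because the inconsistency is plain and the remedy is cheap.

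**What to change.** 1. In Section 8.2.1.4, Table 8 and the Imaging Charter, score RD, dated at that scan, when a lesion the independent reader identified at baseline shows unequivocal growth by RECIST 1.1 progression criteria. If the Charter already has such a rule, cite it. If the sponsor prefers to leave the primary definition unchanged after termination, apply the rule as a DFS sensitivity analysis.
2. Record the independent baseline read as disease or no disease for every woman, and add a DFS sensitivity analysis that excludes those read as having disease. The grouping uses a pre-treatment scan, so it does not condition on outcome.
3. State in Sections 11.2.3 and 11.2.6 that biopsy-positive recurrence under Table 8, and its date, counts in primary DFS, or reconcile the sections in another explicit way.

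Cost: wording in the protocol, Charter and SAP, and limited re-scoring of archived scans by the existing readers. If independent baseline reads were not recorded for all 110 women, those reads must be added. No new scans or patient contact are needed. The downside is a small departure from a pure new-disease definition.
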